7.7.1.2 Supportive Care Guidelines for Binimetinib

Hypertension

It is recommended that additional blood pressure monitoring occur for participants who may be at risk (participants with hypertension at baseline) or those with antecedents of hypertension or those treated with antihypertensive medication. Early initiation of treatment is recommended after diagnosis, with aggressive management of emergent hypertension.

Nausea and/or vomiting

Because nausea and vomiting have been reported for binimetinib, it is recommended that participants are educated on the possibility of occurrence of these side effects prior to starting study treatment. Participant education as well as proper management of nausea and/or vomiting at the first sign is important. Clinical judgment and experience of the treating physician should guide the management plan of each participant. Participants experiencing nausea and/or vomiting CTCAE Grade ≥ 1 should receive antiemetics at the discretion of the treating physician (as per local guideline). It is recommended that participants be provided a prescription for antiemetics, and are instructed on the use of antiemetics on the first day of study drug treatment. Prophylactic antiemetics such as dexamethasone 8 mg, prochlorperazine, or metoclopramide may be administered to participants on an "as needed" basis.

Dose interruption/reduction decisions for nausea and/or vomiting should be based on the CTCAE grade of the toxicity and the guidelines provided in Section 7.2.1.

As guidance for recommendations on supportive measures for the prevention and/or management of nausea and/or vomiting, the published recommendation from ASCO [Sepulveda, A. R., et al 2017], ESMO [Van Cutsem, E., et al 2016], and MASCC can be used [Basch, E., et al 2011] [Roila, F., et al 2010].

Diarrhea

In order to effectively manage diarrhea and mitigate the escalation in severity or duration of diarrhea, participant education as outlined above as well as proper management of diarrhea is important.

Management of diarrhea should be instituted at the first sign of abdominal cramping, loose stools or overt diarrhea. All concomitant therapies used for treatment of diarrhea must be recorded on the Concomitant Medications section of the participant record. It is recommended that participants be provided loperamide tablets and are instructed on the use of loperamide on the first day of binimetinib treatment. In addition to the binimetinib-induced diarrhea dosing guidelines, these instructions should be provided at each visit and the site should ensure that the participant understands the instructions.

Explain the frequency of diarrhea and its relationship to NCI CTCAE grading.

Rule out other or concomitant causes which may include:

- Infection with *Candida*, *Salmonella*, *Clostridium difficile*, *Campylobacter*, *Giardia*, *Entamoeba* and *Cryptosporidium* species can lead to severe infections in immunosuppressed participants
- Medication-induced diarrhea
- Malabsorption/lactose intolerance
- Fecal impaction, partial bowel obstruction

For uncomplicated Grade 1/2 diarrhea

- Stop all lactose-containing products, alcohol and eat frequent small meals that include bananas, rice, applesauce, or toast)
- Stop laxatives, bulk fiber (ie, Metamucil®) and stool softeners (eg, docusate sodium; Colace®)
- Stop high-osmolar food supplements such as Ensure® Plus and Jevity® Plus (with fiber)
- Drink 8 to 10 large glasses of clear liquids per day (eg, water, Pedialyte®, Gatorade® or broth)
- Consider administration of standard dose of loperamide: initial administration 4 mg, then 2 mg every 4 hours (maximum of 16 mg/day) or after each unformed stool
- Discontinue loperamide after 12-hours diarrhea-free (Grade 0) interval
- If uncomplicated Grade 1 to 2 diarrhea persists for more than 24 hours, escalate to high dose loperamide: 2 mg every 2 hours (max. of 16 mg/day) or after each unformed stool.

Note: Oral antibiotics may be started as prophylaxis for infections under the discretion of the physician.

- If uncomplicated Grade 1 to 2 diarrhea persists after 48 hours of treatment with loperamide, discontinue loperamide and begin a 2L agent which can be an opiate (opium tincture or paregoric), octreotide acetate or steroid (budesonide).

For complicated Grade 1/2 diarrhea or any Grade 3 to 4 diarrhea

- The participant must call the investigator immediately
- If loperamide has not been initiated, initiate loperamide immediately. Initial administration 4 mg, then 2 mg every 4 hours (maximum of 16 mg/day) or after each unformed stool.
- Administer IV fluids and electrolytes as needed. In case of severe dehydration, replace loperamide by octreotide.
- Monitor/continue IV fluids and antibiotics as needed. Intervention should be continued until the participant is diarrhea free for at least 24 hours.
- Hospitalization may need to be considered.

Note: (see Section 7.2.1.2 for pembrolizumab dose modification)

Skin Toxicity

Clinical judgment and experience of the treating physician should guide the management plan of each participant. In general, the following interventions are in addition to the rash dosing adjustment guidelines in [Table 7](#):

- Prophylaxis of skin toxicity to be initiated 24 hours prior to the first treatment with study drug or later as needed.
- Application of topical agents to the most commonly affected skin areas such as face, scalp, neck, upper chest and upper back.

Topical agents include non-oily sunscreen (PABA free, SPF \geq 30, UVA/UVB protection), topical steroids (preferably mometasone cream ie, Elocon[®]) and topical erythromycin (ie, Eryaknen[®] or topical pimecrolimus).

Note: Topical agents should be applied on a daily basis starting on Day 1 of study treatment or 24 hours prior to the first dose, and more often as needed.

- Possibly oral doxycycline (100 mg daily) for the first 2-3 weeks of study drug administration.

Other effective medications are antihistamines, other topical corticosteroids, other topical antibiotics and low-dose systemic corticosteroids.

The treatment algorithm based on CTCAE grade is as follows:

Mild rash (CTCAE Grade 1)

- Consider prophylactic rash treatment if not already started.
- Topical or other topical corticosteroid (ie, mometasone cream) and/or topical antibiotic (ie, erythromycin 2%) are recommended.
- The participant should be reassessed within a maximum of 2 weeks or as per investigator opinion.

Moderate rash (CTCAE Grade 2)

- Use of topical erythromycin or clindamycin (1%) plus topical mometasone or pimecrolimus cream (1%) plus oral antibiotics such as: lymecycline (408 mg QD], doxycycline (100 mg BID) or minocycline (50 to 100 mg QD).
- Although there has been no evidence of phototoxicity or photosensitivity in participants being treated with binimetinib, doxycycline (or minocycline as 2L) should be used with thorough UV protection (ie, avoidance of direct exposure to sunlight, use of sunscreen and sunglasses).
- Use of acitretin is not recommended

Severe rash (CTCAE Grade 3-4)

CTCAE Grade 3

- In addition to the interventions recommended for moderate rash, consider oral prednisolone at a dose of 0.5 mg/kg. Upon improvement, taper the dose in a stepwise manner (25 mg for 7 days, subsequently decreasing the dose by 5 mg/day every day).
- Alternatively, in addition to the interventions recommended for moderate rash, consider oral isotretinoin (low doses, ie, 0.3 to 0.5 mg/kg) [Lacouture, M. E., et al 2011].
- Use of acitretin is not recommended.

CTCAE Grade 4

- Immediately discontinue the participant from study drug and treat the participant with oral and topical medications (see recommendation CTCAE Grade 3).

Symptomatic Treatment:

- It is strongly recommended that participants who develop rash/skin toxicities receive symptomatic treatment:
 - For pruritic lesions, use cool compresses and oral antihistaminic agents
 - For fissuring, use Monsel's solution, silver nitrate, or zinc oxide cream. If not sufficient use mild steroid ointments or combinations of steroids and antibiotics such as Fucicort®
 - For desquamation, use emollients with mild pH 5/neutral (best containing urea 10%)
 - For paronychia, antiseptic bath and local potent corticosteroids, use oral antibiotics and if no improvement is seen, refer to a dermatologist or surgeon
 - For infected lesions, obtain bacterial and fungal cultures and treat with topical or systemic antibiotics based on sensitivity of culture

7.7.1.3 Supportive Care Guidelines for mFOLFOX7

Please refer to local guidelines and the label regarding supportive care for participants treated with SOC chemotherapies.

7.7.1.4 Supportive Care Guidelines for FOLFIRI

Participants should receive appropriate supportive care measures as deemed necessary by the site investigator including but not limited to the items outlined below:

Early Diarrhea:

- Occurring during or shortly after infusion of irinotecan is usually transient and infrequently severe. Early diarrhea may be prevented or treated. Consider prophylactic or therapeutic administration of 0.25 mg to 1 mg of IV or subcutaneous atropine (unless clinically contraindicated).

Late Diarrhea:

- Occurring more than 24 hours after administration of irinotecan. Use loperamide 4 mg at the onset of diarrhea, then 2 mg every 2 hours until the participant is diarrhea-free for at least 12 hours.

Colitis/Ileus:

- Participants experiencing ileus should receive prompt antibiotic support.

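### Cohort E falls under two loperamide instructions that differ on daily maximum and duration (Sections 7.7.1.2 and 7.7.1.4), and the protocol does not say which governs

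*Combined protocol and SAP*

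**What the plan says.** Section 7.7.1.4 defines late diarrhea by timing alone: "Occurring more than 24 hours after administration of irinotecan". Its instruction is "Use loperamide 4 mg at the onset of diarrhea", "then 2 mg every 2 hours until the participant is diarrhea-free for at least 12 hours". It states no daily maximum, no maximum duration and no distinction by grade.

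Section 7.7.1.2 has three loperamide regimens, each with a ceiling of 16 mg per day:

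- Uncomplicated Grade 1/2, standard dose: "initial administration 4 mg, then 2 mg every 4 hours (maximum of 16 mg/day) or after each unformed stool".
- Uncomplicated Grade 1/2 lasting more than 24 hours: "escalate to high dose loperamide: 2 mg every 2 hours (max. of 16 mg/day) or after each unformed stool".
- Complicated Grade 1/2, or any Grade 3 to 4, if loperamide has not yet been started: "Initial administration 4 mg, then 2 mg every 4 hours (maximum of 16 mg/day) or after each unformed stool".

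It also limits duration: "If uncomplicated Grade 1 to 2 diarrhea persists after 48 hours of treatment with loperamide, discontinue loperamide and begin a 2L agent".

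Cohort E receives pembrolizumab, FOLFIRI and binimetinib (Section 5.1). The opening of Section 7.7.1 sends events that cannot be attributed to one component to the general recommendations that follow it, without ranking them. Section 7.2.1.1 allows attribution to a single drug and, for overlapping toxicity, consultation with the Sponsor. It concerns dose modification and does not rank the loperamide rules.

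**The concern.** Two instructions for the same drug, the same symptom and the same participants should not give different answers on how much may be taken in a day and when to stop. In Cohort E they do.

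Attribution does not separate them reliably. Section 3.3.1.3 names diarrhea as common with both FOLFIRI and binimetinib. The FOLFIRI rule starts from time since irinotecan and the binimetinib rule from the first symptoms, so neither waits for a causality judgement. FOLFIRI is given every 14 days, so on a literal reading about 14 − 1 = 13 of every 14 days count as late under Section 7.7.1.4.

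Participant safety is at stake. Section 7.7.1.2 recommends that participants be given loperamide tablets with instructions on the first day of binimetinib, and Section 9.1.8.1 makes study treatment outpatient. A Cohort E site has to give the participant one rule to take home, and the protocol supplies two.

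**Working it through.** The 16 mg per day is a stated ceiling, not a derived figure. The check is therefore whether each schedule fits under it.

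**Inputs**

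- FOLFIRI (7.7.1.4): 4 mg, then 2 mg every 2 hours, no maximum.
- Binimetinib (7.7.1.2), standard dose and complicated or Grade 3 to 4: 4 mg, then 2 mg every 4 hours, ceiling 16 mg per day.
- Binimetinib (7.7.1.2), high dose: 2 mg every 2 hours, ceiling 16 mg per day.

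**Formula.** Total = first dose + 2 mg × number of repeat doses before the end of the period. The day is counted as 24 hours from the first dose, and a dose falling exactly at hour 24 belongs to the next day.

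**Binimetinib section**

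- Every 4 hours, first 24 hours: repeats at hours 4, 8, 12, 16 and 20, so 4 + 5 × 2 = 14 mg. This fits under 16 mg.
- Every 2 hours: 12 × 2 = 24 mg per 24 hours if there were no ceiling. The ceiling is reached after 16 / 2 = 8 doses, so it binds.

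**FOLFIRI section, continued dosing**

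- Through hour 12: 4 + 6 × 2 = 16 mg.
- Through hour 14: 4 + 7 × 2 = 18 mg, the first total above 16 mg.
- First 24 hours: 4 + 11 × 2 = 26 mg. Excess 26 − 16 = 10 mg; ratio 26 / 16 = 1.625.
- Each later 24 hours: 12 × 2 = 24 mg. Excess 24 − 16 = 8 mg; ratio 24 / 16 = 1.5.
- First 48 hours: 4 + 23 × 2 = 50 mg, against 2 × 16 = 32 mg under the ceiling.

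**How long an episode must last.** Dosing under Section 7.7.1.4 continues through a 12-hour interval without diarrhea. The dose at hour 14 is therefore due whenever diarrhea is still present later than 14 − 12 = 2 hours after the first dose, provided doses are taken round the clock.

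**Side by side for Cohort E**

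| Item | 7.7.1.2 (binimetinib) | 7.7.1.4 (FOLFIRI) |
|---|---|---|
| Daily maximum | 16 mg in all three regimens | None stated |
| Interval, complicated or Grade 3 to 4 | Every 4 hours, or by stool | Every 2 hours |
| Uncomplicated Grade 1 to 2 persisting after 48 hours of loperamide | Stop; change to a second-line agent | Continue |
| Diarrhea-free end point, complicated or Grade 3 to 4 | 24 hours | 12 hours |

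The 24-hour end point stands in the item on intravenous fluids and antibiotics, so whether it also governs loperamide is itself unclear. The 48-hour row does not depend on any dose total: one section stops loperamide and the other continues it.

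**The case against.** The strongest reply is that both sections are guidance. Section 7.7.1.4 lists measures to be used as the investigator judges necessary, the standard-dose item in Section 7.7.1.2 is something to consider, and Section 7.7 leaves necessary treatment to the investigator. Silence on a maximum is also not permission to exceed one: a site could apply the 16 mg ceiling to the FOLFIRI schedule. The 26 mg is an upper figure that needs uninterrupted dosing. This stands as far as it goes. It means the ceiling conflict arises only in longer episodes, so it would be wrong to say that no site could ever satisfy both sections. It does not remove the conflict. The late-diarrhea sentence is an instruction with its own stopping rule, and importing the ceiling leaves the 48-hour disagreement in place.

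Three stronger readings may suggest themselves, and the documents do not support them.

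- *That Section 7.7.1.2 contradicts itself*, because 2 mg every 2 hours would come to 24 mg. The interval and ceiling stand in one instruction, so dosing stops at 16 mg. A ceiling that binds is not an inconsistency. The wording that allows a dose after each unformed stool leaves some doubt about what the ceiling covers, but that is a minor ambiguity.
- *That the choice of rule would change dose-limiting toxicity (DLT) classification.* For Grade 3 diarrhea, the exception in Section 5.1.3 turns on whether anti-diarrheals were used according to standard of care. It does not refer to a milligram total or define optimal supportive care by either section. A participant on either rule has used an anti-diarrheal. An effect on the primary endpoint is conjecture.
- *That the conflict extends to all five cohorts*, because Table 1 flags diarrhea in each. Cohorts A and C have no FOLFIRI, Cohort D has no binimetinib and Cohort B has neither.

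**Conclusion.** The point holds for Cohort E. The two sections disagree on the daily maximum, on whether loperamide continues after 48 hours in uncomplicated Grade 1 to 2 diarrhea and, for complicated or Grade 3 to 4 diarrhea, on the interval and apparently the diarrhea-free end point. Nothing in the protocol says which prevails.

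On the ceiling, the difference is up to 10 mg in the first 24 hours (26 against 16 mg) and 8 mg in each later 24 hours (24 against 16 mg), starting at hour 14. These figures assume round-the-clock dosing as written in Section 7.7.1.4, no 12-hour diarrhea-free interval in the period counted, and a day counted from the first dose. Shorter episodes or missed night doses give less.

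This is a consistency point between two supportive-care instructions that bears on participant safety. It does not touch the sample size, the estimators or, on the evidence of the documents, the DLT endpoint. No view is taken here on which instruction is right.

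**What to change.** Reconcile Sections 7.7.1.2 and 7.7.1.4 for participants receiving both FOLFIRI and binimetinib, or add a sentence stating which section governs in Cohort E. Either way, the text should settle four items: daily maximum, dosing interval, maximum duration before changing treatment, and diarrhea-free stopping point (including whether the 24-hour interval in Section 7.7.1.2 applies to loperamide). The sponsor must decide the values. Take-home instructions for Cohort E should then match.

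The cost is amendment wording and an update to participant instructions. No change to the design, sample size or analysis is needed.

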7.8 Treatment After the End of the Study

There is no study-specified treatment following the end of the study.

7.9 Clinical Supplies Disclosure

This trial is open-label; therefore, the participant, the trial site personnel, the Sponsor and/or designee are not blinded. Study treatment (name, strength or potency) is included in the label text; random code/disclosure envelopes or lists are not provided.

8. Discontinuation/Withdrawal Criteria

8.1 Discontinuation of Study Treatment

Discontinuation of study treatment does not represent withdrawal from the study.

As certain data on clinical events beyond study treatment discontinuation may be important to the study, they must be collected through the participant's last scheduled follow-up, even if the participant has discontinued study treatment. Therefore, all participants who discontinue study treatment prior to completion of the protocol-specified treatment period will still continue to participate in the study as specified in Section 2 - SoA and Section 9.10.3 – Discontinued Participants Continuing to be Monitored in the Study.

Participants may discontinue study treatment at any time for any reason or be dropped from the study treatment at the discretion of the investigator should any untoward effect occur. In addition, a participant may be discontinued from study treatment by the investigator or the Sponsor if study treatment is inappropriate, the trial plan is violated, or for administrative and/or other safety reasons. Specific details regarding procedures to be performed at study treatment discontinuation are provided in Section 9.1.9 – Withdrawal/Discontinuation.

A participant must be discontinued from study treatment but continue to be monitored in the study for any of the following reasons:

- The participant or participant's legally acceptable representative requests to discontinue study treatment.
- The participant has a confirmed positive serum pregnancy test
- The participant is non-compliant with study treatment or procedures
- The participant has confirmed radiographic disease progression with the exception of the Sponsor approving treatment continuation as outlined in Section 9.2 - Efficacy Assessments

- The participant experiences unacceptable AEs as described in Section 9.3 - Adverse Events, Serious Adverse Events and Other Reportable Safety Events
- The participant develops an intercurrent illness other than another malignancy that prevents further administration of treatment
- The investigator decides to withdraw the participant
- The participant experiences recurrent Grade 2 pneumonitis
- Discontinuation of treatment may be considered for participants who have attained a confirmed CR by local investigator assessments and have been treated for at least 8 cycles (at least 24 weeks), receiving 2 cycles of the combination including 2 doses of pembrolizumab and at least 80% of the planned doses of binimetinib beyond the date when the initial CR was declared. SOC chemotherapies may continue administered at the discretion of the investigator.
- Noncompliance with study treatment or procedure requirements
- The participant experiences progression or recurrence of any malignancy or any occurrence of another malignancy that requires active treatment
- The participant completes 35 treatments (approximately 2 years) with pembrolizumab.
Note: The number of treatments is calculated starting with the first dose.

For participants who are discontinued from study treatment but continue to be monitored in the trial, see Section 2 – SoA, and Section 9.10.3 – Discontinued Participants Continuing to be Monitored in the Study for those procedures to be completed at each specified visit.

Participants may be allowed to begin study treatment again if deemed medically appropriate.

8.2 Withdrawal from the Study

A participant must be withdrawn from the study if the participant or participant's legally acceptable representative withdraws consent from the study.

If a participant withdraws from the study, they will no longer receive study treatment or be followed at scheduled protocol visits.

Specific details regarding procedures to be performed at the time of withdrawal from the study, as well as specific details regarding withdrawal from Future Biomedical Research are outlined in Section 9.1.9 – Withdrawal/Discontinuation. The procedures to be performed should a participant repeatedly fail to return for scheduled visits and/or if the study site is unable to contact the participant are outlined in Section 8.3.

8.3 Lost to Follow Up

If a participant fails to return to the clinic for a required study visit and/or if the site is unable to contact the participant, the following procedures are to be performed:

- The site must attempt to contact the participant and reschedule the missed visit. If the participant is contacted, the participant should be counseled on the importance of maintaining the protocol-specified visit schedule.

- o The investigator or designee must make every effort to regain contact with the participant at each missed visit (eg, phone calls and/or a certified letter to the participant's last known mailing address or locally equivalent methods). These contact attempts should be documented in the participant's medical record.
- o Note: A participant is not considered lost to follow-up until the last scheduled visit for the individual participant. The amount of missing data for the participant will be managed via the pre-specified data handling and analysis guidelines.

9. Study Assessments and Procedures

- Study procedures and their timing are summarized in the SoA.
- Adherence to the study design requirements, including those specified in the SoA, is essential and required for study conduct.
- All screening evaluations must be completed and reviewed to confirm that potential participants meet all eligibility criteria. The investigator will maintain a screening log to record details of all participants screened and to confirm eligibility or record reasons for screening failure, as applicable.
- Procedures conducted as part of the participant's routine clinical management (eg, blood count) and obtained before signing of ICF may be utilized for screening or baseline purposes provided the procedure met the protocol-specified criteria and were performed within the time frame defined in the SoA.

The approximate amount of blood collected from each participant over the duration of the study, including any extra assessments can be found in the procedures manual.

Repeat or unscheduled samples may be taken for safety reasons or for technical issues with the samples.

